8.1 Discontinuation of Study Treatment

Subjects (or a legally acceptable representative) can decline to continue receiving investigational product and/or other protocol-required therapies or procedures at any time during the study but continue participation in the study. If this occurs, the investigator is to discuss with the subject the appropriate processes for discontinuation from investigational product or other protocol-required therapies and must discuss with the subject the possibilities for continuation of the Schedule of Activities (see Section 2.2) including different options of follow-up (eg, in person, by phone/mail, through family/friends, in correspondence/communication with other treating physicians, from the review of medical records) and collection of data, including endpoints, adverse events, as applicable and must document this recommendation in the subject's medical records. Subjects who have discontinued investigational product and/or other protocol-required therapies or procedures should not be automatically removed from the study. Whenever safe and feasible, it is imperative that subjects remain on-study to ensure safety surveillance and/or collection of outcome data.

Subjects may be eligible for continued treatment with Amgen investigational product(s) and/or other protocol-required therapies by a separate protocol or as provided for by the local country's regulatory mechanism, based on parameters consistent with Section 12.3

Approvec

Reasons for removal from protocol-required investigational product(s) or procedural assessments include any of the following:

- Decision by Sponsor
- Lost to follow-up
- Death
- Ineligibility determined
- Protocol deviation
- Non-compliance
- Adverse event
- Subject request
- Pregnancy
- Protocol-specified criteria (Hepatotoxicity Stopping Rules and Mental Health Criteria Stopping Rules); see Section 7.4 and Section 12.8

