9.2.3.6 Suicidal Risk Monitoring

Liraglutide is considered to be a central nervous system (CNS)-active study treatment. In addition, there have been some reports of suicidal ideation and behavior when it has been given to some subjects with obesity. The sponsor considers it important to monitor for such events before and during this clinical study.

It is unknown whether AMG 598 may be associated with an increased risk of suicidal ideation or behavior.

Subjects being treated with AMG 598 and/or liraglutide must be monitored appropriately and observed closely for suicidal ideation and behavior or any other unusual changes in behavior. Consideration is to be given to discontinuing AMG 598 and/or liraglutide in subjects who experience signs of suicidal ideation or behavior.

Families and caregivers of subjects being treated with AMG 598 and/or liraglutide are to be instructed to monitor subjects for the emergence of unusual changes in behavior, as well as the emergence of suicidal ideation and behavior, and to report such symptoms immediately to the study investigator.

Baseline assessment of suicidal ideation and behavior and treatment-emergent suicidal ideation and behavior will be assessed during the study using C-SSRS and Patient Health Questionnaire 9 (PHQ-9). Refer to Section 12.9 and 12.10 for more information.

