Both Amgen and the Investigator reserve the right to terminate the Investigator's participation in the study according to the Clinical Trial Agreement. The investigator is to notify the IRB/IEC in writing of the study's completion or early termination and send a copy of the notification to Amgen.

Subjects may be eligible for continued treatment with Amgen investigational product(s) by an extension protocol or as provided for by the local country's regulatory mechanism. However, Amgen reserves the unilateral right, at its sole discretion, to determine

whether to supply Amgen investigational product(s) and by what mechanism, after termination of the study and before the product(s) is/are available commercially.

Compensation

Any arrangements for compensation to subjects for injury or illness that arises in the study are described in the Compensation for Injury section of the Informed Consent that is available as a separate document.

12.4 Appendix 4. Safety Events: Definitions and Procedures for Recording, Evaluating, Follow-up and Reporting

Definition of Adverse Event

Adverse Event Definition

- An adverse event is any untoward medical occurrence in a clinical study subject irrespective of a causal relationship with the study treatment.
- Note: An adverse event can therefore be any unfavorable and unintended sign (including an abnormal laboratory finding), symptom, or disease (new or exacerbated) temporally associated with the use of a treatment, combination product, medical device or procedure.

Events Meeting the Adverse Event Definition

- Any abnormal laboratory test results (hematology, clinical chemistry, or urinalysis) or other safety assessments (eg, electrocardiogram, radiological scans, vital signs measurements, change in mental health questionnaire scores), including those that worsen from baseline, that are considered clinically significant in the medical and scientific judgment of the investigator (ie, not related to progression of underlying disease).
- Exacerbation of a chronic or intermittent pre-existing condition including either an increase in frequency and/or intensity of the condition.
- New conditions detected or diagnosed after study treatment administration even though it may have been present before the start of the study.
- Signs, symptoms, or the clinical sequelae of a suspected drug-drug interaction.

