Results in persistent or significant disability/incapacity

The term disability means a substantial disruption of a person's ability to conduct normal life functions. This definition is not intended to include experiences of relatively minor medical significance such as uncomplicated headache, nausea, vomiting, diarrhea, influenza, and accidental trauma (eg, sprained ankle) which may interfere with or prevent everyday life functions but do not constitute a substantial disruption.

Is a congenital anomaly/birth defect

Other medically important serious event

Medical or scientific judgment is to be exercised in deciding whether serious adverse event reporting is appropriate in other situations such as important medical events that may not be immediately life-threatening or result in death or hospitalization but may jeopardize the subject or may require medical or surgical intervention to prevent 1 of the other outcomes listed in the above definition. These events are typically to be considered serious.

Examples of such events include invasive or malignant cancers, intensive treatment in an emergency room or at home for allergic bronchospasm, blood dyscrasias or convulsions that do not result in hospitalization, or development of drug dependency or drug abuse.

Recording Adverse Events and Serious Adverse Events

Adverse Event and Serious Adverse Event Recording

- When an adverse event or serious adverse event occurs, it is the responsibility of the investigator to review all documentation (eg, hospital progress notes, laboratory, and diagnostics reports) related to the event.
- The investigator will then record all relevant adverse event serious adverse event information in the Event case report form (CRF).
- The investigator must assign the following adverse event attributes:
 - o Adverse event diagnosis or syndrome(s), if known (if not known, signs or symptoms);
 - Dates of onset and resolution (if resolved);
 - Severity (or toxicity defined below);
 - Assessment of relatedness to Investigational product: (AMG 598/placebo), and/or non-Amgen non-investigational other protocol-required therapy (liraglutide) and/or any study-mandated activity/procedure
 - o Action taken.
- It is not acceptable for the investigator to send photocopies of the subject's medical records to Amgen in lieu of completion of the Event CRF page.

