 - Symptoms (if applicable) including right upper quadrant pain, hypersensitivity-type reactions, fatigue, nausea, vomiting and fever
 - Prior and/or concurrent use of alcohol, recreational drugs and special diets
 - Concomitant use of medications (including non-prescription medicines and herbal and dietary supplements), plants, and mushrooms

- Viral serologies
- Creatine phosphokinase, haptoglobin, lactate dehydrogenase and peripheral blood smear
- Appropriate liver imaging if clinically indicated
- Appropriate blood sampling for pharmacokinetic analysis if this has not already been collected
- Hepatology consult (liver biopsy may be considered in consultation with a hepatologist)

Follow the subject and the laboratory tests (ALT, AST, TBL, INR) until all laboratory abnormalities return to baseline or normal or considered stable by the investigator. The "close observation period" is to continue for a minimum of 4 weeks after discontinuation of all investigational product(s) and protocol-required therapies.

The potential DILI event and additional information such as medical history, concomitant medications and laboratory results must be captured in the corresponding CRFs.

Subjects with an increase in score on either the PHQ-9 and/or CSSR-S assessments

may meet the criteria for permanent discontinuation of Amgen investigational product or

other protocol-required therapies.

Criteria for Withholding and/or Permanent Discontinuation of Amgen Investigational Product and Other Protocol-required Therapies Due to Potential Mental Health Changes

The following stopping rules apply to subjects for whom an increase in their PHQ-9

and/or CSSR-S sores have been identified.

Table 12-3. Conditions for Permanent Discontinuation of Amgen InvestigationalProduct and Other Protocol-required Therapies Due to Changes in Mental HealthScores

Mental Health Assessment	Permanent Discontinuation
PHQ-9	≥ 10
	OR
CSSR-S	Answers yes to any items #1-5

PHQ-9 = Patient Health Questionnaire 9; CSSR-S = Columbia Suicide Severity Rating Scale

Reporting

To facilitate appropriate monitoring for signals of mental health changes according to the criteria specified in the above, require the following:

- The event is to be reported to Amgen as a serious adverse event within 24 hours of discovery or notification of the event (ie, before additional etiologic investigations have been concluded)

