- The appropriate Case Report Form (CRF) (eg, Event CRF) that captures information necessary to facilitate the evaluation of treatment-emergent liver abnormalities is to be completed and sent to Amgen

Additional Clinical Assessments and Observation

All subjects in whom investigational product(s) or protocol-required therapies is/are withheld permanently due to potential mental health changes as specified in Table 12-3 are to undergo a period of "close observation" until the subject's care can be transferred to an appropriate mental health professional.

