12.9 Appendix 9. Columbia Suicide Severity Rating Scale

Baseline Form (shown below) at screening visit and Since Last Visit Form at all subsequent visits.

COLUMBIA-SUICIDE SEVERITY RATING SCALE

(C-SSRS)

Baseline

m

Version 1/14/09

Posner, K.; Brent, D.; Lucas, C.; Gould, M.; Stanley, B.; Brown, G.; Fisher, P.; Zelazny, J.; Burke, A.; Oquendo, M.; Mann, J.

Disdaimer:

This scale is intended to be used by individuals who have received training in its administration. The questions contained in the Columbia-Suicide Severity Rating Scale are suggested probes. Ultimately, the determination of the presence of suicidal ideation or behavior depends on the judgment of the individual administering the scale.

Definitions of behavioral suicidal events in this scale are based on those used in The Columbia Suicide History Form, developed by [name] and [name], Conte Center for the Neuroscience of Mental Disorders (CCNMD), New York State Psychiatric Institute, [name]. (Oquendo M. A, Halberstam B. & Mann J. J., Risk factors for suicidal behavior: utility and limitations of research instruments. In M.B. First [Ed.] Standardized Evaluation in Clinical Practice, pp. 103 -130, 2003.)

For reprints of the C-SSRS contact [name]., New York State Psychiatric Institute, [name]; inquiries and training requirements contact [contact]

© 2008 The Research Foundation for Mental Hygiene, Inc.

Ask questions 1 and 2. If both are negative, proceed to "Suicidal Behavior" section. If the answer to question 2 is "yes", ask questions 5, 4 and 5. If the answer to question 1 and/or 2 is "yes", complete "Intensity of Ideation" section below.			Lifetime: Time He/She Felt Most Suicidal	
 Wish to be Dead. Subject endorses thoughts about a wish to be dead or not alive anymore Have you wished you were dead or wished you could go to sleep and n 		Ves	No	
If yes, describe		-		
 Non-Specific Active Suicidal Thoughts General, non-specific thoughts of wanting to end one's life/countit suic oneself associated methods, intent, or plan. How you accually had any thoughts of killing yourself? 	cide (e.g., "Twe thought about killing my self") without thoughts of ways to kill	Yes □	No □	
If ves, describe				

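### Table 12-3 makes suicidal ideation on the C-SSRS a reason for permanent discontinuation but has no trigger for suicidal behaviour

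*Protocol*

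**What the plan says.** Table 12-3 in Appendix 8 (Protocol Section 12.8) lists two conditions for permanent discontinuation, joined by OR: a PHQ-9 score of at least 10, or, for the C-SSRS, "Answers yes to any items #1-5". Section 8.1 includes among the reasons for removal from investigational product "Protocol-specified criteria (Hepatotoxicity Stopping Rules and Mental Health Criteria Stopping Rules); see Section 7.4 and Section 12.8". Two further steps in Appendix 8 depend on the same criteria. The event must be reported as serious within 24 hours. Subjects whose treatment is "withheld permanently due to potential mental health changes as specified in Table 12-3" go under close observation until a mental health professional can take over.

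At entry, Section 6.2 treats the two constructs separately. Exclusion 216 identifies C-SSRS items 1-5 as suicidal ideation, and exclusion 215 bars any lifetime attempt or suicidal behaviour.

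On study, Section 9.2.3.6 states: "Baseline assessment of suicidal ideation and behavior and treatment-emergent suicidal ideation and behavior will be assessed during the study using C-SSRS" and the PHQ-9. It requires close observation for both ideation and behaviour, and adds: "Consideration is to be given to discontinuing AMG 598 and/or liraglutide in subjects who experience signs of suicidal ideation or behavior". Appendix 9 specifies the forms: "Baseline Form (shown below) at screening visit and Since Last Visit Form at all subsequent visits". Only the Baseline form is reproduced.

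Appendix 4 supplies the general safety rules. A "change in mental health questionnaire scores" is an adverse event if the investigator considers it clinically significant. An intentional overdose with possible suicidal intent is reportable whatever its consequences. For other medically important events, "Medical or scientific judgment is to be exercised in deciding whether serious adverse event reporting is appropriate in other situations", with the comment that such events are typically serious.

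**The concern.** The entry criteria cover ideation and behaviour, but only ideation was carried into the on-treatment stopping table. Read literally, a wish to be dead (item 1, the mildest item) meets the table, while an attempt or a preparatory act with ideation denied does not. The finding that most clinicians would rank as more serious then depends on individual judgment for discontinuation, for the 24-hour report and for the observed handover.

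What is at stake is consistent protection of subjects. Section 5.2.2 plans about 30 sites for cohort 7, so different investigators could handle the same act differently. Section 3.3.3.1 calls liraglutide CNS-active and says it is unknown whether AMG 598 is.

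**Working it through.** The plan gives no figure on this point. The check is mainly a comparison of rules, followed by a rough sizing.

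**1. Which results meet Table 12-3?**

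| Result at a visit | Table 12-3 met? | Appendix 8 stop, 24-hour report and handover |
|---|---|---|
| Item 1 yes, no behaviour | Yes | Apply |
| Interrupted or aborted attempt, or preparatory act; items 1-5 no; PHQ-9 < 10 | No | Not triggered |
| Actual attempt; items 1-5 no; PHQ-9 < 10 | No | Not triggered |

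The PHQ-9 row is not a dependable backstop. Its self-harm item scores 0 to 3 (Appendix 10), so that item cannot reach 10 alone.

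**2. Can the uncovered result be recorded?** On the printed Baseline form, the rater goes to the behaviour section when questions 1 and 2 are both negative. That section is unnumbered and covers actual, interrupted and aborted attempts and preparatory acts. Behaviour with ideation denied is thus a possible entry. The Since Last Visit form used after screening is not printed, so its routing is inferred, but Section 9.2.3.6 does say that treatment-emergent behaviour is assessed with the C-SSRS.

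**3. Does any other rule make discontinuation mandatory?**

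- Section 9.2.3.6: close observation is mandatory, but discontinuation is only to be considered, for ideation and behaviour alike.
- Section 8 and 8.1: the investigator or sponsor may withdraw a subject, and an adverse event is a permitted reason. Both are discretionary.
- Appendix 4: the overdose rule and the medically-important-event rule concern reporting, not stopping.
- Table 7-2: applies to cohorts 1-6 at cohort level and needs a suspected adverse drug reaction.

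None requires the individual subject to stop because of behaviour alone.

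**4. Size.** The documents give no event rate. Assume a probability p of 0.1% to 1% per subject between day 1 and day 207, spread evenly over 206 days. Section 5.4 of this protocol version (Amendment 3) sets the cohort 7 dose from data reviewed at DLRM #4, so cohort 7 (60 subjects) is the cohort still to be dosed. Its C-SSRS visits after day 1 are days 29, 57, 85 and 207 (Table 2-3). Day 85 is the last before end of study, and so the last at which a result could change liraglutide.

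- Expected by day 85: 60 × p × 84/206. For p = 0.001 this is 0.024; for p = 0.01 it is 0.245.
- Chance of at least one: 1 − (1 − p × 84/206)^60 = 2.4% to 22%.
- Expected by day 57, the last dose of AMG 598 or placebo: 60 × p × 56/206 = 0.016 to 0.163.
- Expected over all follow-up, relevant to the 24-hour report: 60 × p = 0.06 to 0.60.

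These are upper bounds on what a new row would change, because they count every event, including those in which drug would be stopped or a report filed on judgment. Exclusions 212-216 point to the low end of the assumed range.

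**The case against.** The strongest reply is that the protocol already protects this subject. Section 9.2.3.6 makes close observation compulsory for behaviour and has families instructed to report symptoms at once. Appendix 4 requires an intentional overdose with possible suicidal intent to be reported, and steers medically important events towards serious status and the 24-hour report. Section 7.4.2 adds ongoing medical monitor review and, for cohort 7, a Safety Surveillance Team. The uncovered case is also narrow. The behaviour probes overlap the ideation items (the attempt probe asks whether the subject wanted to die even a little), so behaviour would usually come with a yes that already meets Table 12-3.

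All of this stands, and it limits the point. A reader might infer that ideation stops treatment with no judgment at all while behaviour is left wholly to discretion. The documents do not support so sharp a contrast. The contents list describes the Appendix 8 actions as suggested, the lead-in to Table 12-3 says subjects with a score increase may meet the criteria, the C-SSRS itself rests on the rater's judgment, and the wording in Section 9.2.3.6 about considering discontinuation covers ideation too.

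The reply does not supply the missing trigger. Appendix 8 also says its stopping rules apply, and Section 8.1 lists them as protocol-specified criteria. That status extends to ideation and to the PHQ-9 score, but not to behaviour. Nor does a discretionary stop bring in the rest of Appendix 8, because the report and the handover are tied to the Table 12-3 criteria.

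**Conclusion.** The gap is real and minor. Suicidal behaviour with items 1-5 denied and PHQ-9 below 10 does not trigger the Appendix 8 discontinuation, 24-hour report or observed handover by rule, and no other text makes discontinuation mandatory. Mandatory close observation and judgment-based stopping and reporting remain, so it would be wrong to conclude that such a subject would go unwatched or would be kept on drug.

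Under the assumed 0.1% to 1% event probability, the affected number in cohort 7 by day 85 is at most about 0.02 to 0.25 subjects. That rests on an unsourced rate, an even spread over time, and the inference that the unprinted Since Last Visit form separates ideation and behaviour as the Baseline form does.

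The planned analysis is unaffected. SAP Section 9.6.2 tabulates suicide/self-injury as an event of interest using a broad search, so a reported event is counted whether or not drug is stopped.

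**What to change.** Add one row to Table 12-3: *OR any positive C-SSRS suicidal behavior item (actual, interrupted or aborted attempt, or preparatory acts)*. The Appendix 8 discontinuation, reporting and observation steps then apply to behaviour as they do to ideation.

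This needs no new assessment or visit, since Section 9.2.3.6 already has treatment-emergent behaviour assessed with the C-SSRS. The downside is a rare extra discontinuation, no more than the 0.02 to 0.25 subjects in cohort 7 under the assumed rates.

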206	A corrected QT interval (QTc) at screening of > 450 msec in males or > 470 msec in females or history of long QT syndrome.
207	For cohorts 2, 4, 6, and 7, screening calcitonin \geq 50 ng/L
208	For cohorts 2, 4, 6, and 7 subjects with a family or personal history of medullary thyroid carcinoma or multiple endocrine neoplasia type 2; a personal history of non-familial medullary thyroid carcinoma; confirmed chronic pancreatitis or idiopathic acute pancreatitis, or gallbladder disease (ie, cholelithiasis or cholecystitis) not treated with cholecystectomy
209	Subjects with a history of renal impairment or renal disease and/or estimated glomerular filtration rate (eGFR) \leq 60 mL/min/1.73 m ²
210	Obesity induced by other endocrinologic disorders (eg Cushing's Syndrome)
211	Previous surgical treatment for obesity (excluding liposuction if performed >1 year before trial entry)
212	History of major depressive disorder
213	History of other severe psychiatric disorders, eg schizophrenia, bipolar disorder
214	A patient health questionnaire (PHQ-9) score of ≥ 10
215	Any lifetime history of a suicidal attempt or of any suicidal behavior
216	Any suicidal ideation as identified by endorsement of (answered yes to) any of the items numbered 1-5 on the Columbia Suicide Severity Rating Scale (C-SSRS)
217	Surgery scheduled for the trial duration period, except for minor surgical procedures, at the discretion of the investigator
218	History of malignancy of any type, other than in situ cervical cancer or surgically excised non-melanomatous skin cancers occurring more than 5 years prior to randomization
219	Positive results for human immunodeficiency virus (HIV) antibodies, hepatitis B surface antigen (HBsAg), hepatitis B core antibody (HBcAb), or hepatitis C virus ribonucleic acid (RNA). For hepatitis C, hepatitis C antibody (HepCAb) testing is done at screening, followed by hepatitis C virus RNA by polymerase chain

reaction (PCR) if hepatitis C antibody is positive

- 220 Subject has systolic blood pressure ≥ 150 mm Hg or diastolic blood pressure ≥ 90 mm Hg (cohorts 1-6) or ≥ 95 mm Hg (cohort 7) at screening, or on day -2 (cohorts 1, 3, 5) or day -1 (cohorts 2, 4, 6) or on day -28 (cohort 7). For each visit, if the initial blood pressure is elevated, the reading may be repeated once at least 15 minutes later and the lower of the 2 readings may be used.

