- Signs, symptoms, or the clinical sequelae of a suspected overdose of either study treatment or a concomitant medication. Overdose per se will not be reported as an adverse event/serious adverse event unless it is an intentional overdose taken with possible suicidal/self-harming intent. Such overdoses are to be reported regardless of sequelae.
- "Lack of efficacy" or "failure of expected pharmacological action" per se will not be reported as an adverse event or serious adverse event. Such instances will be captured in the efficacy assessments. However, the signs, symptoms, and/or clinical sequelae resulting from lack of efficacy will be reported as adverse event or serious adverse event if they fulfill the definition of an adverse event or serious adverse event.

Events NOT Meeting the Adverse Event Definition

- Medical or surgical procedure (eg, endoscopy, appendectomy): the condition that leads to the procedure is the adverse event.
- Situations in which an untoward medical occurrence did not occur (social and/or convenience admission to a hospital).
- Anticipated day-to-day fluctuations of pre-existing disease(s) or condition(s) present or detected at the start of the study that do not worsen.

Definition of Serious Adverse Event

A Serious Adverse Event is defined as any untoward medical occurrence that, meets at least 1 of the following serious criteria:

Results in death (fatal)

Immediately life-threatening

The term "life-threatening" in the definition of "serious" refers to an event in which the subject was at risk of death at the time of the event. It does not refer to an event, which hypothetically might have caused death, if it were more severe.

Requires in-patient hospitalization or prolongation of existing hospitalization

In general, hospitalization signifies that the subject has been detained (usually involving at least an overnight stay) at the hospital or emergency ward for observation and/or treatment that would not have been appropriate in the physician's office or outpatient setting. Complications that occur during hospitalization are an adverse event. If a complication prolongs hospitalization or fulfills any other serious criteria, the event is serious. When in doubt as to whether "hospitalization" occurred or was necessary, the adverse event is to be considered serious. Hospitalization for elective treatment of a pre-existing condition that did not worsen from baseline is not considered an adverse event.

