9.6.2 Adverse Events

The Medical Dictionary for Regulatory Activities (MedDRA) version 20.1 or later will be used to code all events categorized as adverse events to a system organ class and a preferred term. The severity of each adverse event will be graded using the clinical severity grading system provided in Appendix B.

The subject incidence of adverse events will be summarized for all treatment-emergent adverse events, serious adverse events (SAE), adverse events leading to withdrawal of investigational product (AMG598 or Placebo) and/or non-investigational product (Liraglutide), fatal adverse events and adverse events of interest (EOI).

Subject incidence of all treatment-emergent adverse events, serious adverse events, adverse events leading to withdrawal of investigational product (AMG598 or Placebo) and/or non-investigational product (Liraglutide), fatal adverse events and adverse events of interest (EOI) will be tabulated by system organ class and preferred term (in which system organ class will be ordered alphabetically and the preferred terms within each system organ class will appear in descending order of frequency).

In addition, summaries of treatment-emergent and serious adverse events by preferred term in any treatment arm will be provided in descending order of frequency.

Summaries of treatment-emergent and serious adverse events will also be tabulated by system organ class, preferred term, and grade.

The subject incidence of treatment-emergent adverse events will be summarized by actual treatment received.

Treatment related treatment emergent adverse events will be further summarized (by system organ class and preferred term) for AMG 598 and liraglutide separately.

Subject incidence of events of interest will also be summarized according to their categories and preferred term. Events of interest of hypersensitivity will be identified using a narrow search/scope in standardized MedDRA query (SMQ). Events of interest of osteoporosis/osteopenia, gastrointestinal nonspecific inflammation and dysfunctional conditions, hyperglycaemia/new onset diabetes mellitus, depression and suicide/self-injury, and peripheral neuropathy will be identified using a broad search/scope in SMQ. Immunogenicity and Injection site reactions will be identified using Amgen-defined MedDRA search strategies.

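### Appendix 8 sends every on-study PHQ-9 or C-SSRS trigger to SAE reporting without the judgment that Appendix 4 asks for, and the SAP does not show such reports apart

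*Protocol*

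**What the plan says.** **Appendix 8 (Protocol Section 12.8).** Table 12-3 lists a PHQ-9 score of 10 or more, or, for the C-SSRS, "Answers yes to any items #1-5". The lead-in limits the scope: "The following stopping rules apply to subjects for whom an increase in their PHQ-9" or C-SSRS score has been identified. The reporting instruction under the table is "The event is to be reported to Amgen as a serious adverse event within 24 hours of discovery or notification of the event". The next bullet asks for the case report form used to evaluate liver abnormalities.

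**Appendix 4 (Protocol Section 12.4).** Among the findings that meet the adverse event definition it lists a "change in mental health questionnaire scores), including those that worsen from baseline, that are considered clinically significant" in the investigator's judgment. On seriousness it says: "A Serious Adverse Event is defined as any untoward medical occurrence that, meets at least 1 of the following serious criteria". Six criteria follow. The only open one, for other medically important events, calls for medical or scientific judgment.

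**Analysis.** Protocol Section 10.3.2.3.1 includes SAEs in the primary safety endpoint. SAP Section 9.6.2 summarizes all SAEs and adds: "Summaries of treatment-emergent and serious adverse events will also be tabulated by system organ class, preferred term, and grade". Neither document says how a report that rests only on a questionnaire threshold is to be shown.

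**The concern.** Appendix 4 asks two questions before a questionnaire result becomes an SAE: is the change clinically significant, and does it meet a seriousness criterion? Appendix 8 asks neither. Two sites that follow the protocol carefully could classify the same PHQ-9 score of 10 differently, depending on which appendix they read.

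What is at stake is the meaning of the SAE count. The trial is small and its primary analysis is descriptive, so a few reports can change the impression given by an arm. The PHQ-9 also scores sleep, energy and appetite. Protocol Section 3.3.3.1 expects reduced food intake with AMG 598 and mentions mild loss of appetite in the first-in-human study, so score-driven reports need not fall evenly between arms. Under Protocol Section 9.2.3.1.4, serious events that are also unexpected and related may be unblinded before regulatory submission. Classification can therefore affect blinding as well as tables.

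**Working it through.** **1. Does the lead-in about an increase narrow the rule?** Not for eligible subjects. Exclusion 214 (Protocol Section 6.2) bars "A patient health questionnaire (PHQ-9) score of ≥ 10", and exclusion 216 bars "Any suicidal ideation as identified by endorsement of (answered yes to) any of the items numbered 1-5" of the C-SSRS. Criteria 239 and 240 (Section 6.4) repeat both up to day 1 for cohort 7. Any later crossing is therefore an increase.

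**2. One result under both appendices.** Take an on-study PHQ-9 of 10, no ideation item endorsed, judged not clinically significant.

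| Question | Appendix 4 | Appendix 8 |
|---|---|---|
| Is it an adverse event? | Not among the listed questionnaire changes | Yes, by implication |
| Is it serious? | Only if a criterion is met | Reported as serious in every case |
| Who decides? | Investigator | The threshold |

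**3. Where the Appendix 8 wording comes from.** The same reporting sentence stands in Section 12.7.1 for liver injury. There it applies to a specific concurrent laboratory pattern, and a further sentence sends other liver events back to the Section 12.4 criteria. Appendix 8 has the first sentence but not the second, and it still names liver abnormalities. That points to carried-over text.

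**4. Route into the tables.** Section 9.2.3.1.1.2 puts SAEs on the Event CRF, and SAP Section 9.6.2 tabulates SAEs without exception. That threshold-only reports reach the SAE tables is an inference from these two places, but nothing in either document stops it. Protocol Section 10.3.2.3.1 also lists summary statistics from the mental health questionnaires. SAP Section 9.6.1 does not mention them, although SAP Section 10 states that there are no changes. The SAP thus specifies no score table beside which such reports could be read.

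**5. Can PHQ-9 reach 10 without mood items?** Items 3, 4, 5, 7 and 8 (sleep, energy, appetite, concentration, psychomotor change) score up to 3 each: 5 × 3 = 15. A total of 10 is possible with zero on items 1, 2, 6 and 9.

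**6. Size.** The plan states no figure for this point. As a check on the formula, its own detection figures reproduce: 1 − 0.95^66 = 96.6% and 1 − 0.90^66 = 99.9%. PHQ-9 and C-SSRS are scheduled four times after the first dose in every cohort (days 29, 57, 85, 207), or 4 × 108 = 432 scorings. No crossing rate is given, so the share r of subjects who ever cross is assumed. Expected reports are n × r, at one per crossing subject, and the chance of at least one is 1 − (1 − r)^n.

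| Assumed r | Expected of 108 | At least one in 108 | Expected of 66 on AMG 598 | At least one in 66 |
|---|---|---|---|---|
| 1% | 1.1 | 66% | 0.7 | 48% |
| 3% | 3.2 | 96% | 2.0 | 87% |
| 5% | 5.4 | 99.6% | 3.3 | 97% |
| 10% | 10.8 | >99.9% | 6.6 | 99.9% |

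These rows count every Table 12-3 trigger, including ideation that may be serious on its own merits. The number of score-only reports would be lower.

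**The case against.** The strongest reply is that Appendix 8 states a deliberate, cautious designation. A sponsor may decide in advance that certain events are medically important, as Appendix 7 does for the liver pattern. A Table 12-3 trigger leads to permanent discontinuation and close observation until care is handed to a mental health professional, and the protocol cites reports of suicidal ideation with liraglutide. Ideation items 1 to 5 include active ideation with intent or a plan, which may well qualify as medically important. This stands. A reader might infer that Appendix 8 makes events serious in breach of the seriousness criteria. The documents do not support that, because the open criterion can cover many of these events. What remains is that one appendix is automatic where the other asks for judgment.

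Appendix 4 also does not say that other score changes cannot be adverse events; it lists the clinically significant ones as qualifying. Few investigators would dismiss a score that ends treatment. This narrows the conflict, mainly to PHQ-9 of 10 or more alone, but does not remove it.

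A reader might also infer that the true SAE rate would be hidden. That goes too far. SAP Section 9.6.2 shows SAEs by system organ class and preferred term, and has a separate event-of-interest category for depression and suicide/self-injury. Each cohort has concurrent placebo under the same rule. The sample SAE form records the seriousness criterion, but its code for other medically important events would cover threshold-only reports and judged events alike, so it does not separate them. The overall SAE count remains mixed.

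**Conclusion.** The inconsistency is real and limited. Any on-study Table 12-3 trigger must be reported as an SAE with no judgment step, while Appendix 4 works through clinical significance and a listed criterion. The reference to liver abnormalities is an error on any reading. The overall SAE count in the primary safety endpoint can therefore mix threshold-only reports with events that meet an Appendix 4 criterion.

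The size is unknown. The table above rests wholly on assumed crossing rates, and the entry criteria exclude major depressive disorder, other severe psychiatric disorders and any suicidal behavior, which argues for the lower rows. A per-scoring rate compounded over four visits would need the scorings to be independent; positive correlation within a subject would lower the number affected. The absence of SAEs among 56 first-in-human subjects is not a usable benchmark: that was a single-dose study, followed only to day 15 in the 560 mg cohort, and nothing shows that it applied this reporting rule.

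**What to change.** **Protocol.** Reconcile Appendices 4 and 8 on how Table 12-3 triggers are classified, keeping the 24-hour notification. Two consistent solutions are open to the sponsor: Appendix 4 names these triggers as designated medically important events, or Appendix 8 refers seriousness back to Section 12.4. This point takes no side between them, nor on the thresholds or the discontinuation rule. Replace the reference to liver abnormalities.

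**SAP Section 9.6.2.** Tabulate Table 12-3 triggers by arm in their own table, with PHQ-9 and C-SSRS shown separately. Show SAE incidence with and without reports whose only basis is a Table 12-3 trigger. Define how those reports are identified, and apply the definition before treatment assignments are used in the analysis. This display is useful whichever classification is chosen.

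**Cost.** A few lines in two appendices, a flag on the SAE records concerned, and one extra table at the primary and final analyses. No safety notification is lost.
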